5.3.2. Exclusion criteria

There are no exclusion criteria apart from patients who have objected to the collect of their data.

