2. SYNOPSIS

Title:	A Retrospective, Observational, Multicenter, Study to Collect Clinical Safety and Performance data on POLYTHESE® vascular prostheses
Study Population :	Subjects who did receive POLYTHESE® at least one year ago for replacement or bypass of pathological arteries. 3 main sub-populations will be studied depending on location of surgery (thoracic or abdominal and peripheral), but data will be collected for all subjects who did receive POLYTHESE® vascular prosthesis.
Study Design:	Multi-center retrospective case series
Study Type:	PMCF
Number of subjects:	Data from a minimum of 300 subjects will be evaluated. A minimum of 200 subjects will be evaluated for thoracic location of surgery.
Follow-up	At least 1-year follow-up after surgery until a maximum of 5 years.
Study Product:	Any POLYTHESE® vascular prosthesis of following ranges: 
 - POLYTHESE® IC - POLYTHESE® ICT - POLYTHESE® IC-3GL
Intended use:	POLYTHESE® vascular prostheses are indicated for replacement or bypass of arteries presenting aneurysm or arterial disease. Their indication is restricted to thoracic, abdominal and peripheral surgery not involving the crossing of the knee flexion crease.
Objectives:	
 • Describing safety and performance of POLYTHESE® throughout its expected lifetime
Performance primary endpoint:	Primary patency rate at 1 year after surgery using POLYTHESE®
Safety Primary endpoints:	
 • Mortality rate at 30 days after surgery using POLYTHESE®
Performance secondary endpoints:	
 • Procedural success rate • Primary patency rate at 30 days and 6 months after surgery using POLYTHESE® • Primary assisted patency rate at 30 days, 6 months and 1 year after surgery using POLYTHESE® • Secondary patency rate at 30 days, 6 months and 1 year after surgery using POLYTHESE®

PROTOCOL	2021-PT-01
TITLE:	Safety and Performance of POLYTHESE® vascular prosthesis
EFFECTIVE DATE:	1 July 2021
	
 • Device failure during procedure or at discharge, at 30 days, 6 months and 1 year after surgery using POLYTHESE®

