5.3. Subjects

The participating hospitals will screen all potential subjects and will select those who are appropriate for study inclusion, i.e. subjects implanted with POLYTHESE® for at least one year, or with complete data to death. As the study explores real world data, there is no exclusion criteria for subjects and all subjects with POLYTHESE® implanted for at least one year and have not objected to the collect of their data will be included in the study.

All data will be retrieved from medical charts for each patient from time of surgery (considered as index date) until a maximum of 5 years after surgery.

Data from a minimum of 300 from 3 to 8 different sites in France will be evaluated. A minimum of 200 subjects with thoracic location of surgery will be evaluated.

Not more than 50% of study total enrolled subjects shall pertain to one unique centre.

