5.3.1. Inclusion criteria

Patients must meet the following inclusion criteria in order to be eligible for inclusion in the study:

- Patient has a minimum of 1-year post-operative follow-up data available, or complete data to death

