13. INFORMED CONSENT PROCESS

An information letter explaining the purpose of this PMCF study will be sent to patients who meet the inclusion criteria. In accordance with the MR-004, the collection of data of patients who have not objected this collect will be initiated.

The completion of this process will be recorded in study documentation.

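### Objection, the only stated exclusion, is open in practice only to patients who have survived a year, so on its own it shifts 30-day to 1-year mortality slightly upward; the number of objectors should be counted and the shift bounded

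*Protocol*

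**What the plan says.** Objection is the only item under the exclusion criteria in section 5.3.2: "There are no exclusion criteria apart from patients who have objected to the collect of their data".

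Section 13 says how objection comes about: "An information letter explaining the purpose of this PMCF study will be sent to patients who meet the inclusion criteria". It is an opt-out, since "the collection of data of patients who have not objected this collect will be initiated", and section 13 ties it to the French reference methodology MR-004. Completion of this process is to be recorded, but nothing says that objections are counted or reported.

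The inclusion criterion in section 5.3.1 reads "Patient has a minimum of 1-year post-operative follow-up data available, or complete data to death". Section 5.3 describes the eligible set as "subjects implanted with POLYTHESE® for at least one year, or with complete data to death", and then says that "all subjects with POLYTHESE® implanted for at least one year and have not objected to the collect of their data will be included", without repeating the clause on deaths.

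The primary safety endpoint in the synopsis is "Mortality rate at 30 days after surgery using POLYTHESE"; mortality at discharge, 6 months and 1 year is secondary. Section 9.4 calculates proportions on non-missing observations without imputation. Section 8.1 on sample size gives a minimum of 300 subjects, 200 of them thoracic, on grounds of feasibility.

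**The concern.** Whether a patient can leave the study by objecting depends on the outcome being measured. The letter goes out after eligibility is established, so a living addressee is a 1-year survivor. A patient who died within 30 days or within a year cannot reply. Objection by living patients therefore takes people out of the mortality denominators and none out of the numerators at 30 days, 6 months and 1 year.

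This touches the primary safety endpoint. A larger sample does not reduce it. It could also differ between the 3 to 8 sites, and between locations of surgery, if objection rates differ. The protocol gives no means of telling how large it is, because objectors never enter the database and no count is requested.

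**Working it through.** **Inputs.** The protocol states no expected mortality and no objection rate, so there is no figure of its own to reproduce. The following are assumptions, shown as ranges:

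- p30 and p1, true 30-day and 1-year mortality: 5%/10%, and 8%/15% as a second case.
- q, objection rate among 1-year survivors: 1% to 20%.
- l, share of deaths dropped because data to death are incomplete: 0% to 20%.

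Mortality here means the proportion who died.

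**Step 1: objection alone (l = 0).** Of N operated patients, N(1-p1) survive one year and Nq(1-p1) of these object. N[1-(1-p1)q] remain, and every death is still among them. So

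observed mortality = p / (1 - (1-p1)q),

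with p the true rate at 30 days, 6 months or 1 year. The factor uses p1 at every time point, because only 1-year survivors can object.

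Example with N = 1,000, 5%/10% and q = 5%: 900 survivors, 45 objectors, 955 retained. Then 50/955 = 5.24% and 100/955 = 10.47%.

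| q | 30-day, true 5% | 1-year, true 10% | 30-day, true 8% | 1-year, true 15% |
|---|---|---|---|---|
| 1% | 5.05% | 10.09% | 8.07% | 15.13% |
| 2% | 5.09% | 10.18% | 8.14% | 15.26% |
| 5% | 5.24% | 10.47% | 8.36% | 15.67% |
| 10% | 5.49% | 10.99% | 8.74% | 16.39% |
| 20% | 6.10% | 12.20% | 9.64% | 18.07% |

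At 5%/10%, q of 1% to 10% adds 0.05 to 0.49 points at 30 days and 0.09 to 0.99 points at 1 year.

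**Step 2: against sampling error.** The 95% half-width is 1.96 × sqrt(p(1-p)/n). At 5% it is 2.47 points for n = 300 and 3.02 for n = 200. At 10% it is 3.39 and 4.16.

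**Step 3: with incomplete deaths also dropped.** Section 5.3.1 admits a death only with complete data to death. Then

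observed p1 = p1(1-l) / [p1(1-l) + (1-p1)(1-q)].

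For p1 = 10% and q = 5%:

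- l = 0: 0.100/(0.100 + 0.855) = 10.47%
- l = 5%: 0.095/(0.095 + 0.855) = 10.00%
- l = 10%: 0.090/(0.090 + 0.855) = 9.52%
- l = 20%: 0.080/(0.080 + 0.855) = 8.56%

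The two effects cancel when l = q, and the sign reverses when l exceeds q. Dropping survivors who lack a year of data pushes mortality up again, by an amount equally unknown.

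**Step 4: what adding objectors back does.** In the example of step 1, 50/(955 + 45) = 5.00% and 100/(955 + 45) = 10.00%, so the component is removed exactly. With l = 10%, 90 deaths are left among 945 patients, and adding 45 objectors gives 90/990 = 9.09%. That is further from the true 10% than the unadjusted 9.52%. The row isolates one component and does not repair the others.

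**The case against.** The strongest objection concerns direction. A reader might infer that reported mortality will come out too high. The documents do not support that: objection is the only listed exclusion but not the only selection step, and section 5.3.1 removes deaths with incomplete data. Step 3 shows that this can cancel or reverse the effect. The second sentence of section 5.3, read literally, could drop early deaths as well. This objection stands, and it limits the point to objection taken alone.

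A reader might also infer that every death stays in and that no objection can concern a deceased patient. Only deaths with complete data stay in. The protocol does not say how letters to deceased patients are handled or whether relatives may object. Adding all objectors back as survivors would then be wrong for some, so living objectors must be counted separately.

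The effect is also small and unfavourable to the device, and section 8.1 plans no hypothesis test and no mortality threshold. All of that is correct, and it sets the severity.

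Finally, a flow count and a sensitivity row are often left to the SAP, which was not available here, and the protocol misstates nothing. This stands for the row. It carries less weight for the count: objections arise while the letters are being answered, and if sites are not asked for counts by location then, a later SAP may be unable to recover them.

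**Conclusion.** The point holds in a limited form. Under the opt-out process, exclusion by objection of living patients depends on survival and, taken alone, can only raise mortality at 30 days, 6 months and 1 year, by the factor 1/(1-(1-p1)q). For objection rates up to 10% and assumed mortality of 5%/10%, the rise is below half a point at 30 days and below one point at 1 year, well inside the confidence interval for 200 or 300 patients. It passes one point at 30 days only near q = 20% (6.10% against 5%), a rate for which the documents give no support.

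The size rests wholly on assumed rates. The net bias in reported mortality is of unknown sign. The opt-out is not an error and should not be removed. Low severity: worth acting on because it touches the primary safety endpoint and can be bounded from an aggregate count.

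**What to change.** 1. In section 13, have each site report aggregate counts by location of surgery: patients screened; patients objecting, with objections by living patients kept apart from any made on behalf of deceased patients; and patients ineligible for incomplete data. Show these in the subject flow.

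2. Keep the main analysis as planned. Add to section 8.1 (Statistical design, method and analytical procedures) wording such as: *As a sensitivity analysis, mortality at 30 days, 6 months and 1 year is also given, overall and by location of surgery, with living objectors added to the denominator as survivors. This bounds the effect of objection only and does not correct for patients excluded for incomplete data.*

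3. Stop the row at 1 year. Beyond that, an objector's vital status at a given time no longer follows from eligibility.

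The cost is one short count form per site and one extra row in the mortality tables. No individual data on objectors are needed, and the opt-out under MR-004 is unchanged. If the counts turn out low, the sponsor can show that this component is negligible.

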6. RISKS AND BENEFITS OF THE DEVICE

6.1. Anticipated clinical benefits

There is no clinical benefit expected from the study as the evaluated device is already commercially available and used in routine, and as there will be no extra procedure for subjects who have been already implanted and followed. The study will only analyse already collected data.

There is no anticipated additional clinical benefit expected from the use of POLYTHESE® devices rather than other commercially available similar devices with same indications for use.

Anticipated clinical benefits of the device are thus equivalent to anticipated clinical benefits of open surgical vascular repair of thoracic, abdominal and peripheral arteries.

PROTOCOL	2021-PT-01
TITLE:	Safety and Performance of POLYTHESE® vascular prosthesis
EFFECTIVE DATE:	1 July 2021

Replacement or bypass of arteries presenting obliterative arterial disease is required to restore the function of the artery: restore the blood flow to distal tissues. Anticipated clinical benefits may consist in patient's symptoms relief, improved quality of life and reduced tissular ischemia, amputation and mortality risks.

Replacement or bypass of arteries presenting dissection and/or aneurysmal disease is required to exclude the false lumen entry tear(s) and/or aneurysmal part without compromising the blood flow to distal tissues. Anticipated clinical benefits may consist in reduced risks of dissection and/or aneurysm associated complications and reduced risk of aneurysm rupture and mortality.

6.2. Anticipated risks

There is no risk either associated to the study as there is no procedure performed in the scope of the study. The risks listed below are those related to revascularization surgery and use of grafts and will be the ones monitored

The type and rate of anticipated risks may differ according to indication and location of the surgical procedure, and may result in:

- Medically important event or reaction
- Persistent or significant incapacity or substantial disruption of the ability to conduct normal life functions
- Re-intervention and re-hospitalization or prolongation of existing hospitalization
- Life-threatening event, reaction up to death.

Early (peri-operative) and late adverse events of abdominal aortic and peripheral arteries open vascular repair with POLYTHESE® devices include (but are not restricted to):

- Bleeding
- Hematoma
- Adherence to surrounding tissues
- Allergic reaction
- Inflammatory reaction / oedema
- Seroma / lymphorrea formation
- Wound complications: infection (superficial or deep), revision
- Graft infection
- Graft dilatation
- Pseudo aneurysm / false aneurysm (para-anastomotic aneurysm; non-anastomotic aneurysm)
- Graft stenosis / occlusion
- Limb occlusion
- Amputation (major or minor)
- Secondary aorto-enteric fistula
- Renal dysfunction
- Neurologic deficit
- Pericardial effusion

PROTOCOL	2021-PT-01
TITLE:	Safety and Performance of POLYTHESE® vascular prosthesis
EFFECTIVE DATE:	1 July 2021

- Pulmonary complication (pneumonia, perioperative acute pulmonary oedema)
- Cardiac complications (myocardial infarction or arrhythmia, ischemic heart disease, atrial fibrillation)

7. OBJECTIVES AND ENDPOINTS

The principal objective of the POLYTHESE® study is to describe safety and performance of POLYTHESE®. Identification and analysis of potential emergent risks will be performed according to the availability of the collected adverse events.

Identification of possible systematic misuse or off-label use of POLYTHESE®, with a view to verifying that the intended purpose is correct, will also be performed according to the availability of the data.

The following table summarizes the performance and safety endpoints and timeframe after surgery.

Study endpoints	At surgery	Time period following surgery			
		30 days	6 months	1 year	>1 year until 5 years of follow-up
Performance endpoints					
Primary patency rate*	---	X	X	X*	X
Primary assisted patency rate	---	X	X	X	X
Secondary patency rate	---	X	X	X	X
Device Failure	X	X	X	X	X
Procedural success rate	X	---	---	---	---
Safety endpoints					
Mortality rate*	X	X*	X	X	X
Limb salvage rate	---	X	X	X	X
Adverse events **	X	X	X	X	X

* Primary endpoint

** Listed in section 6.2

7.1. Performance endpoints

Primary performance endpoints are **primary patency rate at 1 year** after surgery using POLYTHESE®.

The others effectiveness endpoints are:

- Procedural success rate, defined as:
 - o Ability to use with no need for replacement by another device and,
 - o Effective vascular flow restoration after procedure and,
 - o In case of aneurysm, exclusion of aneurysmal portion after procedure.

PROTOCOL	2021-PT-01
TITLE:	Safety and Performance of POLYTHESE® vascular prosthesis
EFFECTIVE DATE:	1 July 2021

- Primary patency rate, defined as rate patency of the bypass graft without procedure or intervention of the conduit itself (except for occlusion)
- Primary assisted patency rate, defined as rate patency of the bypass graft with or without procedure or intervention of the conduit itself (except for occlusion) after device implantation
- Secondary patency, defined as rate patency of the bypass graft with or without procedure or intervention of the conduit itself for occlusion after device implantation
- Device Failure, defined as:
 - o Uncontrolled blood leakage from device
 - o Loss of structural integrity, e.g. rupture and/or exaggerated dilation (> 50 %)
 - o Occlusion of the device
 - o Total or partial replacement of the device required

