which used reversed vein and 52 of which used 6-mm **POLYTHESE® IC collagen prosthesis**. When collagen prosthesis was used, operating time was shorter than vein bypass graft (73±9.1 minutes vs. 105±8.8 minutes, $p=0.002$). Two cases with collagen prosthesis had superficial wound infection which did not require reoperation and result in graft loss. None of the patients who had collagen prosthesis were lost to follow-up. Primary patency rates of collagen prosthesis vs. vein bypass graft were 67% vs. 81% ($p=0.065$) at 2-year. After reintervention, the secondary patency rates of autogenous grafts vs collagen prosthesis were 81% vs. 77% ($p=0.298$) at 3-year. The difference between collagen prosthesis and bypass graft in terms of patency rates were not statistically significant due to short follow-up time and longer time is required to see a significant difference. Nevertheless, results suggest that collagen prosthesis can be safely used for femoropopliteal bypass grafting.

Prospective non-randomized single-centre study (published data)

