7.2. Safety endpoints

Primary safety endpoint is **mortality rates at 30 days** after surgery using POLYTHESE®.

- Others study safety endpoints are:
 - o Mortality rate, defined as freedom % from death
 - o Limb salvage rate, defined as freedom % from target limb amputation
 - o Adverse events, defined as any documented adverse events, including anticipated (as listed in section 6.2) and non-anticipated adverse events.

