9.5. Database structuration

After data consistency step, databases will be compiled to one database frozen for analyses. Variables might be created for the analyses.

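### The wording of primary patency, the 1-year primary performance endpoint, exempts interventions for occlusion, so a graft that occluded and was reopened can count as primary patent

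*Protocol*

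**What the plan says.** The Synopsis names the performance primary endpoint, "Primary patency rate at 1 year after surgery using POLYTHESE", and the endpoint table in section 7 marks it as primary. Neither defines it. The definition stands only in section 7.1, which words the three patency measures as follows:

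- Primary: "Primary patency rate, defined as rate patency of the bypass graft without procedure or intervention of the conduit itself (except for occlusion").
- Primary assisted: patency of the graft "with or without procedure or intervention of the conduit itself (except for occlusion) after device implantation".
- Secondary: patency of the graft "with or without procedure or intervention of the conduit itself for occlusion after device implantation".

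The same section lists "Occlusion of the device" among the criteria for device failure.

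Section 9.2 lists the raw items that sites supply: interventions, prosthesis assessments, adverse events and dates. A patency class is not among them. Section 9.5 adds: "Variables might be created for the analyses".

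**The concern.** The same bracket has opposite effects in two adjacent definitions. In the assisted definition it follows a permission (with or without intervention) and removes interventions for occlusion from what is allowed. That is the usual meaning of assisted patency. In the primary definition it follows a prohibition (without intervention) and so allows interventions for occlusion.

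Patency measures are meant to be nested: every primary patent graft is assisted patent, and every assisted patent graft is secondary patent. As worded, a reopened graft passes the strictest measure and fails the middle one. A graft treated for stenosis before it ever occluded fails the strictest measure. The worse course counts as success and the better one as failure.

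The study is descriptive, so the reported rate is its main product. Section 5.2 says that existing evidence does not sufficiently support the performance claims and that the study is needed to keep the device on the European market. A primary rate that includes part of secondary patency would err in the device's favour.

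**Working it through.** The plan has no figure to reproduce. The sample size rests on feasibility, and no patency rate is assumed. The check applies the three definitions to every possible graft history and then counts.

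**Step 1: classify.** I assume one graft per subject and read secondary patency as any graft patent at 1 year.

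| Class at 1 year | Primary, as worded | Primary, uninterrupted | Assisted | Secondary | Device failure by occlusion |
|---|---|---|---|---|---|
| A: never occluded, no intervention on conduit | yes | yes | yes | yes | no |
| B: never occluded, with intervention | no | no | yes | yes | no |
| C: occluded, reopened, patent, no other intervention | **yes** | no | no | yes | yes |
| D: as C, plus another intervention | no | no | no | yes | yes |
| E: not patent | no | no | no | no | yes |

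Only class C changes status. Grafts that occlude again fall in E, and those with a further intervention fall in D; neither is affected.

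**Step 2: formulas.** With N grafts:

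- primary, uninterrupted = A/N
- primary, as worded = (A + C)/N
- assisted = (A + B)/N
- secondary = (A + B + C + D)/N
- excess in the primary rate = (A + C)/N − A/N = C/N, never negative
- primary as worded exceeds assisted only if C > B

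**Step 3: size.** N = 300 and the thoracic minimum of 200 come from the Sample size justification. The shares C/N are assumed, because the protocol gives none.

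| Assumed C/N | Grafts of 300 | Grafts of 200 thoracic | Excess, points |
|---|---|---|---|
| 1% | 3 | 2 | 1.0 |
| 2% | 6 | 4 | 2.0 |
| 5% | 15 | 10 | 5.0 |

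**Step 4: two examples.** All counts are assumed: N = 300, D = 0, E = 6, A = 285.

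| | B = 3, C = 6 | B = 6, C = 3 |
|---|---|---|
| Primary, uninterrupted | 285/300 = 95.0% | 285/300 = 95.0% |
| Primary, as worded | 291/300 = 97.0% | 288/300 = 96.0% |
| Assisted | 288/300 = 96.0% | 291/300 = 97.0% |
| Secondary | 294/300 = 98.0% | 294/300 = 98.0% |

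In the first column the order breaks visibly, with primary above assisted. In the second the reported rates look orderly, yet primary is still 1.0 point too high. An orderly set of results is therefore no proof that the derivation was right.

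**Step 5: what the protocol's earlier data can tell.** The 1-year patencies of 97.1% and 99.7% in section 5.1 do not state the type of patency, so they do not bound C/N. For 52 femoropopliteal grafts of this device, the same section gives primary patency of 67% at 2 years and secondary patency of 77% at 3 years. The time points differ, and the gap may include interventions for other reasons, so it does not estimate the 1-year excess. It does show that the two measures can lie well apart for this device. That summary also puts results following reintervention under the secondary heading ("After reintervention, the secondary patency rates of autogenous grafts vs collagen prosthesis"), which is not what the section 7.1 wording of primary patency does.

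**The case against.** The strongest reply is that the intent is plain. The three definitions form a graded set, occlusion is a device failure in the same section, and earlier results after reintervention are reported as secondary patency. On that reading the bracket is a slip carried over from the assisted line, and a competent analyst would ignore it. The Statistical design section leaves detail to the SAP, and section 9.2 announces a separate document on the data to collect; either may hold a correct derivation. No hypothesis is tested and no performance goal is set. Occlusions stay visible as device failures and adverse events, and assisted and secondary patency are reported at the same time points.

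Much of this stands. The slip is the likely origin, the effect on the reported rate is conditional on the text being followed, and no decision rule is at risk. But an obvious intent does not repair a sentence that says the reverse, and two analysts could defend different primary results once the data are known. The SAP was not available for this review. If it is correct, it conflicts with the protocol. Reporting assisted patency alongside would reveal the error only when C > B.

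**Conclusion.** The definition is wrong as written and should be corrected before the endpoint is derived. Followed literally, it raises 1-year primary patency above uninterrupted patency by exactly the share of grafts that were reopened, are patent at 1 year and were otherwise untouched. The direction is certain. The size is not: 1 to 5 points at an assumed share of 1% to 5%. Section 9.4 drops missing endpoints from the denominator, so the share applies to grafts with a known 1-year status, which may be fewer than 300. The case for correction rests on a defective sole definition of the primary performance endpoint and a nearly free repair, not on a proven large bias.

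**What to change.** In section 7.1, replace the primary patency definition with: *uninterrupted patency with no occlusion and no procedure or intervention on the conduit for any reason since implantation*. Leave the assisted and secondary definitions unchanged. The measures are then nested again: A/N ≤ (A + B)/N ≤ (A + B + C + D)/N. Check that the SAP uses the same definition.

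The cost is one sentence. The interventions, assessments and events needed are already listed in section 9.2. The reported primary rate may be slightly lower.

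A minor correction can go in the same amendment. Section 7.2 has "Mortality rate, defined as freedom % from death", which describes survival. Either rename it or define mortality as the percentage of subjects dead from any cause by the time point. This reclassifies no subject.
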